10.2 Definition of analysis sets

The following analysis sets are defined in accordance with the ICH-E9 guideline¹⁰:

- Full analysis set (FAS): includes all randomised subjects receiving treatment. In exceptional cases subjects from the FAS may be excluded. In such cases the exclusion will be justified and documented. Subjects in the FAS will contribute to the evaluation ‘as treated’.
- Safety analysis set: includes all subjects receiving treatment. Subjects in the safety analysis set will contribute to the evaluation ‘as treated’.

One observation period, “on-treatment”, is defined.

- On-treatment: the observation period from time of initiation of treatment to end of treatment. The on-treatment observation period will be defined separately for each treatment period.

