5.1 Overall design

This trial is an escalation trial with the aim to investigate whether the selected t_{\max} in the algorithm settings will allow safe use of the insulin only bionic pancreas with fast-acting insulin aspart. This trial is a single-centre, sequential-cohort, randomised, single blind, cross-over escalation trial over three cohorts.

For each cohort, eight new subjects will be recruited and randomised. Subjects will be randomised in a 1:1 manner to two treatment sequences i.e. the default t_{\max} setting ($t_{65} = 65$ minutes) followed by the non-default t_{\max} setting ($t_{50} = 50$ minutes, $t_{40} = 40$ minutes or $t_{30} = 30$ minutes) or the non-default t_{\max} setting followed by the default t_{\max} setting, all in combination with fast-acting insulin aspart. The treatment duration is 7 days for each treatment period, (see [Figure 5–1](#)). The subjects will be blinded towards the order of their t_{\max} setting. There are no restrictions of any kind on diet,

exercise, or other activities. Subjects will be asked to keep their diet and activity as normal as possible throughout the trial.

[figure not shown]

Figure 5-1 Trial design

The treatment in this trial is defined as the combination of selected t_{max} setting on the iLet™ with fast-acting insulin aspart. The total treatment duration within each cohort will be 14 days with each cross-over period of treatment being 7 days. No wash-out is implemented between the cross-over periods. Continuation to the next cohort will occur only if the stopping criteria on a cohort level are not met (see section [8.1.1](#) for stopping criteria).

For each subject, an ‘in-patient’ period is implemented for the first 1 day (24 hours \pm 3 hours) following treatment initiation, i.e. at visit 2 and at cross-over visit (visit 3). This entails that subjects will stay at a designated place (such as a hotel) for the specified duration and will be discharged as per PI’s discretion, see section [9.15](#). This period is included in the 7 days treatment period. The ‘out-patient’ period is defined as the period after the discharge from the designated place where the subject stays during the ‘in-patient’ period and until the end of treatment.

[figure not shown]

Figure 5–2 In-patient and Out-patient period

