8.1.1 Escalation stopping criteria

After all subjects have completed Visit 4 in a given cohort, the PI will evaluate if any of the following have occurred in individual subjects:

- Time in low interstitial glucose (defined as below 54 mg/dL (3.0 mmol/L)) is higher than 2% of the total time from initiation of treatment (day 1) to end of treatment (day 7) on the same t_{\max} , or,
- One or more episodes of treatment emergent severe hypoglycaemia (see [Appendix 7](#) for definition) have occurred from initiation of treatment (day 1) to end of treatment (day 7) on the same t_{\max}

For each subject and for each treatment period, the time in low interstitial glucose (percentage) and number of treatment emergent severe hypoglycaemia episodes as per the above evaluation must be recorded in the CRF.

Escalation decision

If any of the above specified events occur in two or more subjects on the same t_{\max} setting within a cohort, continuation to the next cohort with a lower t_{\max} setting will not occur. Concretely, continuation to the next cohort with a lower t_{\max} setting will not occur in the following scenarios:

- Time in low interstitial glucose (defined as below 54 mg/dL (3.0 mmol/L)) is higher than 2% of the total time from initiation of treatment (day 1) to end of treatment (day 7) on the same t_{\max} in two or more subjects,
- One or more episodes of treatment emergent severe hypoglycaemia (see [Appendix 7](#) for definition) have occurred from initiation of treatment (day 1) to end of treatment (day 7) on the same t_{\max} in each of two or more subjects,
- Time in low interstitial glucose (defined as below 54 mg/dL (3.0 mmol/L)) higher than 2% of the total time from initiation of treatment (day 1) to end of treatment (day 7) on the same t_{\max} in one or more subjects and one or more episodes of treatment emergent severe hypoglycaemia (see [Appendix 7](#) for definition) have occurred from initiation of treatment (day 1) to end of treatment (day 7) on the same t_{\max} in one or more subjects.

The escalation decision at the end of the cohort must be documented by the PI. If the escalation decision is to not open the next cohort, then the subjects who are in screening will be registered as withdrawn and an end-of-trial form must be completed.

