8.1.2 Temporary discontinuation of trial treatment

During the temporary discontinuation of trial treatment, subject should be treated as per PI's discretion and the Fiasp[®] pen included in the back-up kit may be used. In a scenario where the iLet[™] is replaced or restarted due to any technical reasons, subject will not be required to have an "in-patient" period again.

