9.11 Self-measured plasma glucose

Subjects will be provided with a BG meter including auxiliaries as well as instructions for use. The subjects will be instructed in how to use the device and the instruction should be repeated, if needed

The BG meters use test strips calibrated to plasma values. Therefore, all measurements performed with capillary blood are automatically calibrated to plasma equivalent glucose values, which will be shown on the display.

The BG meter provided by Novo Nordisk should be used for the measurements required in the protocol. SMPGs must be performed to calibrate the CGM sensor (section [9.10](#)) and in the event of hypoglycaemic episode ([Appendix 7](#)) and should be reported in the diary, see section [9.14](#).

All SMPGs values must be recorded in the paper diary. In addition to paper diary, SMPGs performed for the calibration of the CGM sensor must also be recorded on the StudyPhone with CGM app. The record of each SMPG value on paper diary should include date, time and value. All data from the diary must be transcribed into the CRF during or following the contact.

9.12 iLet™ settings

The glucose target for the iLet™ will be set to 120 mg/dL (6.6 mmol/L). Subjects must be instructed not to change any settings related to BW and glucose target on the iLet™. Temporary targets are not allowed.

Initialisation of iLet™

The iLet™ should be initialised by entering the subject's current BW at visit 2 and visit 3. See section [9.4.1](#) for reporting of BW.

The date and time when the site staff starts the iLet™ at visit 2 and visit 3 will be considered as the time-point for initiation of treatment. This start date and time must be recorded in the CRF.

Stopping of iLet™

The date and time when the site staff stops the iLet™ at visit 3 and visit 4 will be considered as time-point for end of treatment. These stop date and time must be recorded in the CRF.

t_{max} setting

The t_{max} setting in the iLet™ should be set by the site staff at visit 2 and visit 3 as per the subject's randomisation sequence.

Meal announcements

Meal announcements can be entered via a user interface that runs on the iLet™. The user interface allows optional meal announcements, designated as “start of the day”, “middle of the day”, or “end of the day” or “sleeping”, of size “tiny”, “small”, “typical for me” or “large”. Subjects will be recommended to use this feature immediately before eating the main meals of the day, but not snacks.

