Number of self-manageable (able to self-treat) treatment-emergent hypoglycaemic episodes that require oral carbohydrate intervention per day from initiation of treatment (day 1) to end of treatment (day 7) (count)

Treatment emergent self-manageable (able to self-treat) hypoglycaemic episodes that require oral carbohydrate intervention per day will be calculated as the sum of all treatment-emergent hypoglycaemic episodes where the subject is able to self-treat and that require oral carbohydrate intervention divided by the actual duration of the treatment period in days. It will be presented using descriptive statistics made by cohort and treatment.

Number of treatment-emergent adverse events from initiation of treatment (day 1) to end of treatment (day 7) (count)

Adverse events will be coded using the Medical Dictionary for Regulatory Activities (MedDRA) and will be presented based on system organ class and preferred terms.

Treatment-emergent: adverse events will be defined as treatment-emergent, if the onset of the event occurs in the on-treatment period

Treatment-emergent adverse events will be presented in terms of the number of subjects with at least one event (N), the percentage of subjects with at least one event (%), the number of events (E) and the event rate per 100 years of exposure (R) made by cohort and treatment. These summaries are done by seriousness, severity, relation to trial product, adverse events leading to discontinuation of trial treatment and outcome.

Furthermore, summary tables based on system organ class and preferred terms are made for:

- All treatment-emergent adverse events
- Serious treatment-emergent adverse events

- Possibly and probably related treatment-emergent adverse events
- Severe treatment-emergent adverse events

All adverse events will be listed with information on when it occurred.

Number of treatment-emergent infusion site reactions from initiation of treatment (day 1) to end of treatment (day 7) (count)

Treatment-emergent infusion site reactions will be summarised by cohort and treatment.

Total insulin dose (U/kg) per day from initiation of treatment (day 1) to end of treatment (day 7) (U/Kg/day)

Total daily insulin dose will be calculated as the sum of all insulin doses delivered by the iLet™ divided by the actual duration of the treatment period in days. It will be presented using descriptive statistics made by cohort and treatment.

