Treatment-emergent: hypoglycaemic episodes will be defined as treatment-emergent, if the onset of the episode occurs in the on-treatment period (see definition in Section 10.2).

Nocturnal hypoglycaemic episodes: episodes occurring between 00:01 and 05:59 both inclusive.

Hypoglycaemic episodes are classified according to the Novo Nordisk classification of hypoglycaemia and the ADA classification of hypoglycaemia²⁰.

Reporting of hypoglycaemic episodes:

PG should always be measured and recorded when a hypoglycaemic episode is suspected or when a hypo alarm is triggered on the iLet™.

All PG values:

≤3.9 mmol/L (70 mg/dL) or

>3.9 mmol/L (70 mg/dL) occurring in conjunction with hypoglycaemic symptoms should be reported as a hypoglycaemic episode according to the flowchart and instructions below. When a subject experiences a hypoglycaemic episode, subject should record the general information in relation to the hypoglycaemia (timing, PG measurements, symptoms etc. as described in the diary). In case a subject is not able to fill in the diary (e.g. in case of hospitalisation or at the ‘follow-up phone contact’), then investigator should report the hypoglycaemic episode in the CRF.

Upon onset of a hypoglycaemic episode the subject is recommended to measure PG every 15 minutes until the SMPG value is >3.9 mmol/L (70 mg/dL) and/or symptoms have been resolved in accordance with current guidelines²⁰.

Repeated SMPG measurements and/or symptoms, occurring within a period of 60 minutes after onset of a hypoglycaemic episode, will by default be considered as one hypoglycaemic episode until a succeeding SMPG value is >3.9 mmol/L (70 mg/dL) and/or symptoms have been resolved and should be reported on one hypoglycaemic episode form. SMPG measurements ≤3.9 mmol/L (70 mg/dL) or hypoglycaemic symptoms after the 60 minutes period shall trigger the reporting of a new hypoglycaemia episode.

In case of several low SMPG values within the 60 minutes interval, the lowest value is the one that will be reported as the SMPG value for the hypoglycaemic episode but the start time of the episode will remain as the time for the first low SMPG value and/or symptom.

The lowest value measured during the hypoglycaemic episode will be reported as the PG value for the episode. The remaining values will be kept as source data in the diary.

A hypoglycaemic episode starting without symptoms should be updated to symptomatic if the subject experiences symptoms later during the episode.

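### Total daily insulin dose divides iLet-delivered insulin by the whole treatment period, so any time off the iLet understates U/kg/day for the assigned t_max setting

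*Combined protocol and SAP*

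**What the plan says.** **What treatment is.** Section 5.1: "The treatment in this trial is defined as the combination of selected" t_max setting on the iLet with fast-acting insulin aspart. A subject on a pen or on their usual pump is therefore not on trial treatment during that time.

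**The window.** Section 10.2 sets one on-treatment period per treatment period, namely "the observation period from time of initiation of treatment to end of treatment". Under section 9.12, initiation is when site staff start the iLet at visits 2 and 3, and their stopping it "at visit 3 and visit 4 will be considered as time-point for end of treatment". Section 5.1 also describes the two treatment periods as running from visit to visit. None of these places makes an allowance for a stop in mid-period.

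**Foreseen interruptions.** Section 8.1.2: "During the temporary discontinuation of trial treatment, subject should be treated as per" the principal investigator's discretion, with the back-up insulin pen as an option. Amendment 1 adds three routes:
- section 9.10: a temporary stop after inadvertent acetaminophen use;
- section 9.16: a move to usual pump therapy when CGM connectivity cannot be re-established after 6 hours, until site staff can assess device and subject in person (no time limit given);
- section 8.1.4: suspension of iLet treatment for all subjects if a trial stopping criterion is met.

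**The dose endpoint.** Section 10.3.2.1 computes "the sum of all insulin doses delivered by the iLet™ divided by the actual duration of the treatment period in days" and presents it descriptively by cohort and treatment. No model is planned.

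**Related rules.** Appendix 7: "hypoglycaemic episodes will be defined as treatment-emergent, if the onset of the episode occurs in the on-treatment period". The escalation criteria in section 8.1.1 are "One or more episodes of treatment emergent severe hypoglycaemia" and time below 54 mg/dL that "is higher than 2% of the total time from initiation of treatment (day 1) to end of treatment (day 7) on the same" t_max setting.

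**The concern.** The numerator and denominator of the dose endpoint cover different spans of time. A total-insulin quantity would need off-iLet insulin in the numerator. An on-iLet quantity would need off-iLet hours out of the denominator. The formula as written gives neither when an interruption occurs.

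The numerator cannot be completed from the data listed. Off-iLet doses are not among the diary items (section 9.14) or the parameters transferred from the iLet (section 9.12). The concomitant medication fields (section 7.7) record name, indication and dates, but not dose.

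At stake is a supportive descriptive table meant to show how much insulin each t_max setting delivers. A setting with more interrupted time would appear to use less insulin than it does. The same unbroken window also decides which hypoglycaemic episodes are summarised under a t_max setting, and it leaves a question open in the escalation rule.

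**Working it through.** The plan states no figure to reproduce: section 10.1 makes no formal sample size calculation, and no interruption rate is given. The hours off the iLet below are assumptions.

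**Inputs**
- Period length T = 7 × 24 = 168 h (section 5.1). The flowchart's −1 day visit window allows T = 144 h.
- Subjects per cohort: 8, each receiving both settings, with sequences randomised 1:1 (section 5.1).
- h = hours off the iLet in one period (assumed).
- On-iLet rate r = 0.60 U/kg/day (assumed, for illustration only).

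**One subject, one period**

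Insulin delivered by the iLet = r × (T − h)/24. The plan divides this by T/24 days, so

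reported rate = r × (1 − h/T), and relative understatement = h/T.

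| Hours off | T = 168 h | T = 144 h |
|---|---|---|
| 6 | 6/168 = 3.6% | 6/144 = 4.2% |
| 12 | 12/168 = 7.1% | 12/144 = 8.3% |
| 24 | 24/168 = 14.3% | 24/144 = 16.7% |

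Check with r = 0.60, T = 168, h = 24: delivered = 0.60 × 6 = 3.60 U/kg. Divided by 7 days this is 0.514; divided by the 6 days on the iLet it is 0.60.

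**Cohort mean for one setting** (equal r across subjects)
- One of eight subjects off for 24 h: 14.29%/8 = 1.8% too low.
- A 24 h suspension while all eight are in the same period: the 1:1 sequences put about four subjects on each setting. Each setting's mean falls by about (4/8) × 14.29% = 7.1%, with no expected difference between settings.

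**Hypoglycaemic episodes**

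By sections 9.12 and 10.2, a mid-period stop does not end the on-treatment period. By Appendix 7, an episode that starts while the subject is on a pen or usual pump is then treatment-emergent, and it enters the summaries for the t_max setting of that period. One severe episode moves a cell from 0/8 to 1/8 subjects. Exposure is 8 × 7/365.25 = 0.1533 years, so the rate moves from 0 to 1/0.1533 × 100 = 652 per 100 years.

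**Escalation rule, texts side by side**
- Appendix 7 with section 10.2: an off-iLet episode in the window is treatment-emergent.
- Section 8.1.1: both criteria are tied to the same t_max setting, over initiation to end of treatment.
- Section 5.1: treatment is a t_max setting on the iLet, so a subject on usual pump therapy is arguably on no t_max setting.

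The first points to counting the episode and the third points away. Section 8.1.1 contains wording for both and does not settle it.

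**The case against.** **Exposure to interruptions is limited.** Amendment 1 excludes people unwilling or unable to avoid acetaminophen. It sets the connectivity alert at 15 minutes and asks for sensor replacement if recovery fails within 20–30 minutes. Suspension requires at least three subjects with serious adverse events, severe hypoglycaemia or ketoacidosis considered possibly or probably related to the device. This stands and is a main reason to rate the point minor.

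**The word actual in the dose formula might mean net of interruptions.** It is not defined that way, and sections 5.1, 9.12 and 10.2 all point to the full visit-to-visit period. The as-treated wording in section 10.2 says how subjects contribute, and gives no rule within a period.

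**An unbroken window is a defensible safety choice.** Lows soon after a stop may still reflect insulin the iLet delivered. This stands: for hypoglycaemia and CGM measures the full window should remain the main summary. Severe episodes are also SAEs under Amendment 1, with a causality assessment, and adverse events are listed with timing, so an off-iLet episode would be visible among eight subjects.

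**Three stronger readings are tempting, and the documents do not support them.**
- A reader might infer that an off-iLet severe episode automatically supplies one of the two subjects that stop escalation. The tie to the same t_max setting in section 8.1.1 makes this an ambiguity, not a literal trigger.
- A reader might infer that the primary endpoint is contaminated by off-iLet glucose. It uses available values (section 10.3.1) collected on the iLet (section 9.1). The documents do not say whether the iLet logs CGM while stopped, and in the connectivity route there may be no values at all.
- A reader might apply the full 14.3% to a cohort mean under a trial-wide suspension. That would need all eight subjects to be on the same setting at that moment, contrary to what 1:1 sequences give for subjects running concurrently.

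**Conclusion.** The dose mismatch holds on the text. Following section 10.3.2.1 exactly understates U/kg/day by h/168 for an affected subject and period, and by about 1.8% on the cohort mean for 24 hours off in one of eight subjects. It distorts the comparison of settings only if off-iLet time is unequal between them, and it vanishes without interruptions. The formula follows from the plan's definitions; the hours are assumed.

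For hypoglycaemic episodes, the window places off-iLet events under a t_max setting without marking them. That is a reporting gap, not an error in the choice of window. For CGM measures, any effect depends on logging that the documents do not describe. For escalation, section 8.1.1, section 10.2 and Appendix 7 leave open whether off-iLet time counts, and they must be reconciled.

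Severity: minor. The endpoint is supportive and descriptive, in an exploratory trial.

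**What to change.** 1. **Dose (section 10.3.2.1).** Divide by the days the subject was being treated by the iLet under the assigned t_max: the treatment period minus documented temporary discontinuations under sections 8.1.2, 8.1.4, 9.10 and 9.16. Show the full-period figure as a labelled sensitivity table.
2. **Identifying off-iLet time.** Use the site contact records that section 9.16 already requires in the CRF, together with the time-stamped iLet records in section 9.12. The transferred delivery status alone may not be enough, because the documents do not show that it captures every switch to a pen or usual pump. Do not count algorithm-driven zero dosing as time off the iLet: section 3.2.1 describes the algorithm withholding insulin as part of normal operation.
3. **Hypoglycaemic episodes and CGM measures.** Keep the initiation-to-end window as the main safety summary. Flag episodes with onset off the iLet and add an on-iLet-only sensitivity table. For CGM, add it only if values are logged while the iLet is stopped.
4. **Escalation (section 8.1.1).** Reconcile this section with section 10.2 and Appendix 7 on whether episodes and glucose values during a temporary discontinuation count toward the criteria. Which way is for the sponsor and investigator; the 2% threshold and the two-subject count are not in question. This belongs in the protocol, because section 10.3 makes a SAP optional and due only before database lock, whereas escalation is decided after each cohort.

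Cost: one changed denominator, some extra derivation and a few tables, and a wording amendment to section 8.1.1 that may need IRB/IEC approval (Appendix 3).

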10.3 Statistical analyses

If necessary, a statistical analysis plan (SAP) may be written in addition to the protocol, including a more technical and detailed elaboration of the statistical analyses. The SAP will be finalised before database lock.

Endpoints and derivations based on the interstitial glucose profiles will be summarised and analysed using the FAS, unless otherwise stated. The other endpoints will be summarised using the safety analysis set and analysed using the FAS.

